## **History of Modifications**

Modification on Oct 1, 2013: To assure that Best Practices were implemented, a decision was made to have study staff make initial and follow-up referrals of all trial participants in the Best Practices and Best Practices +Financial Incentives conditions to the Vermont Quitline rather than train referring physicians to make those referrals.

Modification on August 15, 2019: In light of evolving guidance on the risk-benefits of breastfeeding among women continuing to smoke, we decided to expand our analyses of breastfeeding to also include the percent breastfeeding while sustaining smoking abstinence.

Modification on January 23, 2020: We replaced proposed low-birth weight as a birth outcome with small-for-gestational-age (<10th percentile) deliveries to reduce potential confounding with differences in gestational age based on information provided in the 2020 U.S. Department of Health and Human Services, *Smoking Cessation: A Report of the Surgeon General*. U.S. Department of Health and Human Services, Center for Disease Control and Prevention, National Center for Chronic Disease Prevention and Health Promotion, Office of Smoking and Health, 2020.

Modification on September 1, 2021. In completing the cost-effectiveness analyses we made updates to reflect guidelines and data sources published since our protocol was originally reviewed by funders

and local IRB in 2013. Our final analyses follow recommendations published in 2016 from the Second U.S. Panel on Cost-Effectiveness in Health and Medicine (Neumann et al. *Cost-effectiveness in Health and Medicine, 2nd edition*. New York: Oxford University Press. 2017). They state that cost-effectiveness analyses should include a provider and/or public payer perspective to better inform producers and payers about the intervention's costs of adoption. In updating our data sources, we incorporated methods used in the only other cost-effectiveness analysis in the peer-reviewed literature on the use of abstinence-contingent financial incentives with pregnant women who smoke (Boyd et al. Are financial incentives cost-effective to support smoking cessation during pregnancy. *Addiction*. 2016; 111(2): 360-70). More specifically, we adopted their method of translating smoking abstinence into QALY gains, which permits QALYs to be derived directly from data available in the trial based on “absolute difference percent” (ADP) (see Stapleton JA, West R. A direct method and ICER tables for the estimation of the cost-effectiveness of smoking cessation interventions in general populations: applications to a new cystine trial and other examples. *Nicotine Tob Res*. 2012; 14(4): 463-71).

The protocol information provided below is what the local Institutional Review Board approved for this randomized clinical trial comparing Best Practices, Best Practices +Financial Incentives, and Never Smokers.

## Project Summary

Smoking during pregnancy is the leading preventable cause of poor pregnancy outcomes in the U.S. Most pregnant smokers continue smoking through pregnancy producing serious immediate and longer-term adverse health consequences for the infant. Smoking during pregnancy is highly associated with economic disadvantage and a substantive contributor to health disparities. Efficacious interventions are available, but cessation rates are low (<15%) and improvements in birth outcomes often modest or absent. Current treatments usually entail relatively brief, low-cost interventions (e.g., pregnancy-specific quitlines). There is broad consensus that more effective interventions are sorely needed. We have developed a novel behavioral economic intervention in which women earn financial incentives contingent on smoking abstinence. In a meta-analysis of treatments for smoking during pregnancy, effect sizes achieved with financial incentives were severalfold larger than those achieved with lower intensity approaches or medications. The intervention also appears to improve birth outcomes and increase breastfeeding duration. While highly promising, further research is needed in at least three areas. (1) The evidence on birth outcomes and breastfeeding is from studies that combined data across trials rather than a single prospective trial, (2) whether the intervention produces other postpartum improvements in health has not been investigated, and (3) the overall cost effectiveness of this approach has not been examined. To examine these unanswered questions, we are proposing a randomized, controlled clinical trial comparing the efficacy and cost effectiveness through one-year postpartum of current best practices for smoking cessation during pregnancy vs. best practices plus financial incentives among 230 pregnant, Medicaid recipients. We will also include a third condition of 115 pregnant nonsmokers matched to the smokers on sociodemographic and health conditions to compare the extent to which the treatments reduce the burden of smoking and to estimate how much more might be accomplished by further improvements in this incentives intervention without exceeding cost effectiveness. We hypothesize that best practices plus financial incentives will be more effective than best practices alone, that the incentives intervention will be cost effective, and that while

adding the incentives reduces a greater proportion of the health and economic burden of smoking than best practices alone, more can be done while remaining cost effective. Overall, the proposed study has the potential to substantially advance knowledge on cost-effective smoking cessation for pregnant women. Importantly, because of the strong association between smoking during pregnancy and economic disadvantage, the proposed study also has the potential to contribute new knowledge relevant to reducing the serious challenges of health disparities.

## **Research Design and Methods**

We proposed a parallel groups design involving three study conditions. Across two of the conditions we will employ a conventional randomized, controlled clinical trial research design comparing outcomes between two treatment approaches to smoking cessation during pregnancy. The third condition will represent a group of women who are biochemically-verified nonsmokers and matched to women in the smoking cessation conditions on characteristics that may influence health and health-care-utilization outcomes.

## **Participants**

Study participants will be 345 pregnant Medicaid recipients > 18 yrs of age who will be recruited from obstetric practices and the WIC office located in the greater Burlington, VT area using procedures developed in our prior trials (e.g., Heil et al., 2008; Higgins et al., 2004b). As noted above, 230 of these women will be smokers and 115 nonsmokers recruited from the same clinics. Pregnant women attending their first prenatal visit will be identified from the appointment schedules. The practices' receptionists will request that women complete a brief self-administered smoking screening form containing a multiple-choice question on smoking status that has been validated to enhance accurate reporting (Mullen et al., 1991). Women who endorse smoking in the 7 days prior to screening will be invited for an intake assessment that will provide a more thorough determination of study eligibility. For inclusion in the cessation trial, women must report being smokers at the time that they learned of the current pregnancy, report smoking in the 7 days prior to the first prenatal care visit, be confirmed as a smoker by urine cotinine testing, be < 25 weeks pregnant, reside in the county in which the clinic is located, speak English, and plan on remaining in the geographical area through 12-months postpartum. Two hundred and thirty eligible smokers who agree to participate and provide written informed consent will be randomly assigned to one of the two treatment conditions described below. Women who endorse no smoking in the 7 days prior to screening will be similarly invited for the same detailed assessment and biochemical verification of smoking status. To be eligible they must report

being nonsmokers at the time they learned of the current pregnancy, report no smoking in the past 6 month, and report smoking < 100 cigarettes in their lifetime, the conventional definition of a never smoker (Pomerleau et al., 2004). Recruiting never smokers will substantially reduce the likelihood of women in this condition converting to smoker status during the study. They must also meet other study inclusion criteria listed above and will be frequency matched to women in the two smoker conditions on the following characteristics that may influence outcomes: (1) maternal education (% < 12 years), (2) pre-pregnancy body mass index (% > 25, % > 30), (3) parity (% primigravida), (4) age (% < 20 yrs), (5) comorbidities (% diabetic, % hypertensive), and (6) recreational use of cocaine/opioids in past 12 months (% reporting yes). Initially, the distributions of these characteristics will be based on our previous trials but where necessary adjustments will be made as smokers are enrolled into the proposed trial. Because women will be recruited at the start of their prenatal care, we will not yet know infant sex and thus will not be able to balance across conditions on that characteristic. We anticipate comparable distribution of infant sex across study conditions, but will include it as a covariate in analyses of birth and infant health outcomes if it differs significantly across study conditions.

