## Statistical Methods

Study conditions will be compared on baseline demographics and other characteristics using analysis of variance for continuous variables and chi-square tests for categorical variables. If a specific characteristic differs significantly across study conditions and is predictive of outcome, it will be considered as a potential covariate in subsequent analyses. Analyses of treatment effects on smoking status will be limited to smokers randomized to the two treatment conditions. We will adhere to an intent-to-treat approach (Armitage, 1983) wherein all women randomized to the study conditions will be included in the analyses independent of early dropout, noncompliance, etc., with the exception of excluding women for abortion/fetal demise as is convention in this research area. Cochran Mantel Haenszel tests (CMH) will be performed for comparisons of the two treatment conditions on point-prevalence smoking abstinence at end-of-pregnancy and 6-months postpartum assessments with

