referring clinic as a stratification variable. The Breslow-Day Test will be used to examine the homogeneity of treatment effects across referring clinics. Comparisons of point-prevalence abstinence rates between treatment conditions across all assessments through one-year postpartum will be analyzed using mixed model repeated measures for categorical data based on generalized estimating equations (GEE) utilizing a logistic link function (SAS: PROC GENMOD, SAS Institute, Cary, NC). We will include women from the nonsmoker condition in analyses of fetal growth, birth outcomes, and breastfeeding and other postpartum outcomes. Comparisons of treatment conditions on dichotomous outcomes (e.g. % low birth weight, % preterm, % NICU admissions, % breastfeeding, % medical treatment in first year) will parallel categorical analyses for point prevalence abstinence using PROC GENMOD to adjust for strata (referring clinics) and potential covariate effects. Analysis of covariance will be used to compare study conditions on mean birth weight adjusting for variables known to predict birth weight (i.e., maternal prepregnancy BMI, parity, and sex), mean gestational age at delivery, and frequency measures of medical illnesses. Statistical analyses of fetal growth outcomes (i.e. estimated fetal weight, fetal lean area, fat area, femur length and head circumference) will be based on linear growth models with slope and intercept as random effects (SAS PROC MIXED). This methodology allows for the within-subjects ultrasound assessments not to be at identical timepoints across subjects. Study condition will be considered a fixed factor with fetus nested within study condition. Two-way analyses of covariance will also be used for analyzing effects of study condition and referring clinic on DEXA body composition measures at 12 months. Additional subject level covariates will include maternal pre-pregnancy body mass index, maternal age and fetal gender. Analyses of infant growth will parallel those used to examine fetal growth. Repeated measures analyses of variance will be used to test for differences between study conditions in skinfold thickness obtained during infant 1st year of life and continuous measures of medical illnesses. Significance will be based on alpha = .05 for all analyses.

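### Never smokers are frequency matched on six factors, but no analysis is pre-specified to include all six, and the baseline-significance rule would usually leave out those that match well.

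*Combined protocol and SAP*

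**What the plan says.** The Participants section states that never smokers "will be frequency matched to women in the two smoker conditions on the following characteristics that may influence outcomes". It lists education, pre-pregnancy BMI (two cut-points), parity, age, comorbidities (diabetes, hypertension) and past-year cocaine/opioid use: six factors, eight binary indicators. The reference is both smoker conditions together, 230 women. Target distributions start from earlier trials, and "where necessary adjustments will be made as smokers are enrolled into the proposed trial".

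Statistical Methods then says: "We will include women from the nonsmoker condition in analyses of fetal growth, birth outcomes, and breastfeeding and other postpartum outcomes". The covariates it names for those analyses are:

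- Birth weight: analysis of covariance "adjusting for variables known to predict birth weight (i.e., maternal prepregnancy BMI, parity, and sex". Two of the six matching factors are included.
- DEXA body composition at 12 months: BMI, maternal age and fetal gender. Two of the six are included. The sentence naming them follows both the fetal-growth and the DEXA descriptions, so it could be read to cover fetal growth too.
- Dichotomous outcomes (preterm birth, NICU admission, breastfeeding and others): "using PROC GENMOD to adjust for strata (referring clinics) and potential covariate effects". No matching factor is named.
- Skinfold thickness: no matching factor is named.

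The general rule for any other covariate is: "If a specific characteristic differs significantly across study conditions and is predictive of outcome, it will be considered as a potential covariate".

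**The concern.** The plan matches on these factors because it believes they may influence outcomes, and then makes their use in the analysis depend on a baseline significance test. Successful matching removes significant differences, so the test tends to exclude the factors that the design balanced. An analysis that omits prognostic factors balanced by design uses a variance that is too large.

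Where matching is imperfect, the same test has little power to flag a moderate imbalance. Matching is on coarse group percentages and acts only at enrolment. Fetal-loss exclusions and dropout before the later postpartum outcomes can undo it.

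The third group is there to show how much of the smoking burden each treatment removes. Fetal growth, birth weight and breastfeeding are listed among the primary hypotheses in Sample Size Justification, with power claimed between any two conditions. At stake are some lost precision in those contrasts and, because the group is not randomised, leftover differences that could be read as smoking burden.

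**Working it through.** **1. The plan's own figure.** Sample Size Justification gives 115 per condition, a birth-weight difference of about 200 g, SD 550 g, two-sided 0.05 and 80% power.

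- SE = 550 × √(2/115) = 72.5 g.
- Power = Φ(200/72.5 − 1.96) = 78.7%. The stated 80% reproduces, given that the difference is described as approximate; 203 g gives 80%.

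**2. What matching to the pooled smokers does to the variance.** Let R² be the share of outcome variance explained by the omitted matching factors. The documents do not give it, so 0.05 to 0.30 is assumed. If never smokers match the pooled 230, their covariate mean is (m1 + m2)/2, where m1 and m2 are the means in the two smoker arms.

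- One arm minus never smokers leaves (m1 − m2)/2. Its variance is one quarter of that between two unmatched groups of 115.
- True variance of the unadjusted contrast = σ² × (2/115) × [(1 − R²) + R²/4] = σ² × (2/115) × (1 − 0.75R²).
- The model reports σ² × (2/115), so the SE is too wide by 1/√(1 − 0.75R²) − 1.
- Test size = 2 × [1 − Φ(1.96/√(1 − 0.75R²))].
- Adjusted SE ≈ 72.5 × √(1 − R²).

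On the birth-weight scale (SD 550 g, difference 200 g):

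| Assumed R² | SE too wide by | Size of nominal 5% test | Power unadjusted | Adjusted SE | Power adjusted |
|---|---|---|---|---|---|
| 0 | 0% | 5.0% | 78.7% | 72.5 g | 78.7% |
| 0.05 | 1.9% | 4.6% | 79.2% | 70.7 g | 80.8% |
| 0.10 | 4.0% | 4.2% | 79.6% | 68.8 g | 82.8% |
| 0.20 | 8.5% | 3.4% | 80.6% | 64.9 g | 86.9% |
| 0.30 | 13.6% | 2.6% | 81.7% | 60.7 g | 90.9% |

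Unadjusted power is Φ[(200 − 1.96 × 72.5)/(72.5 × √(1 − 0.75R²))]. Simulation of pooled matching with assumed factor prevalences gave SE ratios of 1.09 to 1.10 at R² 0.20 and 1.13 to 1.14 at R² 0.30, in line with the formula. For birth weight itself the gain is smaller, because BMI and parity are already in that model.

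**3. What the baseline test lets through.** For a factor of prevalence p, 230 smokers against 115 never smokers, the largest non-significant difference is 1.96 × √[p(1 − p)(1/230 + 1/115)]:

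- p = 0.1: 6.7 points
- p = 0.2: 9.0 points
- p = 0.5: 11.2 points

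If the test is instead one three-group chi-square and the two smoker arms are equal, 1.96 becomes √5.99 = 2.45, and the limits are about 8 points at p = 0.1 and 14 at p = 0.5. The chance of flagging 25% against 20% is 15% with 115 per group (19% with 230 vs 115). For 25% against 15% it is 47% (61%).

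The resulting bias is the imbalance times the factor's effect on the outcome: an 11.2-point imbalance passes on 0.112 of that effect. The documents do not give the effects, so no figure in grams can be stated.

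**4. Dichotomous outcomes.** These use a logistic link. In simulation with two exactly matched groups of 115 (assumed prevalences and effects, 1,000 data sets per setting), the log-odds SE rose on adjustment, from 0.277 to 0.290 and from 0.275 to 0.300 at the two effect strengths tried. Test size was 3.0 to 3.6% unadjusted and 4.1 to 5.0% adjusted. The unadjusted test is mildly conservative, and adjustment does not shrink the log-odds SE.

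**The case against.** The strongest reply is that the plan is not silent and that little is at stake. Matching targets are updated during enrolment, the general covariate rule covers all study conditions, and the dichotomous models allow for potential covariates. The SE error is conservative and creates no false positives. It vanishes if R² is zero, and at R² of 5 to 10% the power gain is only 2 to 3 points. Planned power is roughly met without it: 78.7% for birth weight, and 87.7% and 80.3% for never smokers against incentives on breastfeeding at 12 and 24 weeks.

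Most of this stands as a limit on size. It does not remove the point: the general rule only promises to consider a factor that passes a weak test, and updating targets acts only at enrolment.

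A reader might infer three stronger things that the documents do not support:

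- That imbalance after enrolment will stay uncorrected. The conditional provisions mean only that it may.
- That the full SE excess and substantial imbalance occur together. The first needs matching to hold and the second needs it to fail, so each grows at the other's expense.
- That standard errors are too wide by 1/√(1 − R²) − 1, about 3 to 20% over the same range. That assumes matching to a single arm, whereas the plan matches to both smoker conditions. Nor does the SE argument carry over to the logistic outcomes.

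**Conclusion.** The concern holds in a limited form. No model is pre-specified to carry all six matching factors, three factors are named nowhere, and the rule for adding them would normally pass over a well-matched prognostic factor.

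For continuous outcomes the cost is a conservative SE excess of about 2 to 14%. This rests on an assumed R² of 0.05 to 0.30 for the omitted factors and on matching that holds against the pooled smokers. If matching slips, that cost falls and the issue becomes residual confounding from imbalances of up to about 7 to 11 points that the baseline test would not flag. For dichotomous outcomes, confounding control is the only substantial reason to adjust.

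The randomised comparison on smoking status is untouched, since "Analyses of treatment effects on smoking status will be limited to smokers randomized to the two treatment conditions". The point merits a change because the remedy costs almost nothing and helps whether or not the matching holds.

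**What to change.** In Statistical Methods, state that every comparison involving never smokers includes the six matching factors as fixed covariates whatever their baseline p-values, with BMI and age continuous where available. Where events are few, as may be so for NICU admission or preterm birth, replace them with a single summary score of the matching factors to avoid overfitting. Say explicitly whether the sentence on additional subject-level covariates applies to fetal growth as well as DEXA. Leave the randomised incentives versus best-practices contrast as separately specified.

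The cost is wording, about 8 degrees of freedom out of 345 women, and slightly more analysis work. The factors are already collected for the matching, and the sample size does not change.

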## **Treatment Conditions**

**Best Practices Alone.** The 2008 Clinical Practice Guidelines for smoking cessation recommends that pregnant smokers should be provided with the 5As (Fiore et al., 2008). To ensure that referring obstetric practices in the proposed recruitment area are acquainted with the 5As, our staff will conduct office-based training sessions with all referring practices prior to the start of study recruitment and at least once annually throughout the course of the study using training procedures developed previously by our research team and utilized in our prior studies. Practitioners will be trained to implement the following steps: (1) Ask about smoking status starting at first prenatal care visit; (2) Advise those who endorse smoking about the potential harm of smoking to mother and fetus and recommend quitting; (3) Assess the willingness of smokers to make a quit attempt during pregnancy; (4) Assist those willing to make a quit attempt by helping to establish a quit plan, by referring them to the Vermont pregnancy-

specific quit line described below and offering assistance with making the initial contact from the office, and by providing each woman with a copy of the pregnancy-tailored self-help guide “Need Help Putting Out That Cigarette?”, distributed by the American College of Obstetricians and Gynecologists; (5) Arrange for follow-up contacts on smoking at each subsequent prenatal care visit. They will refer women to the Vermont pregnancy-specific quitline, operated by Free & Clear, which provides eight proactive telephone counseling calls during the antepartum period, with one prior to a quit date, two within the first week of quitting, and the final antepartum call just before the woman’s delivery date. Two additional counseling calls are made during the postpartum period. Calls average about 10 min in length. The quitline makes five attempts to reach the woman within a 3-day period for each scheduled telephone counseling session. We will obtain permission from women to request from Free & Clear the number of telephone counseling sessions completed by each woman during the course of the study.

**Best Practices + Financial Incentives.** Women assigned to this condition will receive the same 5As intervention from providers plus the incentives intervention described above that will be delivered by project staff. Briefly, women report to our smoking-cessation clinic or have a research assistant meet them at a location convenient for them according to a predetermined schedule. At these visits, the women can earn points recorded on vouchers contingent on biochemically-verified abstinence from recent smoking. Abstinence will be assessed for five consecutive days in week 1, decreasing to twice weekly in week 2 where it remains for the next 7 weeks, then decreasing to once weekly for 4 weeks, and then to every other week until delivery. During the postpartum period, abstinence monitoring will be weekly for 4 weeks and then every other week through 12 weeks postpartum at which point the voucher program will be discontinued. The monetary value of vouchers will be kept as they were in our prior trials for women who report smoking < 10 cigs/day at study intake assessment, with the initial negative test specimen worth 5 points at a value of \$1.25 per point (\$6.25). Each consecutive negative test specimen increments the number of points earned by 1 such that the 2nd consecutive

negative specimen is worth 6 points (\$7.50), the 3rd negative specimen 7 points (\$8.75), the 4th specimen 8 points (\$10.00), etc. Voucher value continues to escalate upward based on consecutive negative test results until it plateaus at a maximal value of \$45. A reset contingency is used wherein a positive test or failure to submit a specimen for a scheduled test resets the number of points earned back to the initial 5 points. This reset component of the schedule protects against relapse once an initial period of abstinence has been achieved (Roll & Higgins, 2000). Two consecutive negative tests following a reset returns the number of points earned back to the value that they were at prior to the positive test result. In the postpartum period, voucher value is set at a flat \$45/negative test (36 points) independent of how much abstinence was achieved antepartum. A positive test result or failure to submit a scheduled specimen lowers the voucher value to 5 points (\$6.25), but two consecutive negative tests returns voucher value back to \$45 in the postpartum period. Total possible earnings for a woman who participated in the voucher program for 32 weeks antepartum (duration varies depending on where in the pregnancy a woman enters prenatal care) and 12-weeks postpartum and sustained abstinence throughout is \$1,225 (\$865 antepartum & \$360 postpartum). For women who report smoking > 10 cigs/day at the study intake assessment the schedule described above will be identical except that voucher value will be increased 2-fold at each step such that maximal total earnings = \$2,450 (\$1,730 antepartum & \$720 postpartum). Because vouchers are only paid out when women are abstinent, we project mean payouts of \$613 and \$1,226 across 9 months or approximately \$2.27/day and \$4.54 /day across the lower and higher voucher values. Women will not be informed of our criteria for determining who receives higher value incentives. We have conducted prior trials with differing voucher values among substance abusers without difficulty by explaining that interventions are individualized just as medications dosages often are (Higgins et al., 2007a). We anticipate being able to do so in the proposed study. Regarding use of pharmacotherapies, our practice is to explain to women the risks and benefits of using them but recommend against their use because they have not yet been shown to be effective among pregnant women and may interfere with the opportunity to earn

vouchers through cross reactivity with urine cotinine testing. We will monitor use of all such products so that their use could be considered as a potential covariate in the data analysis. There has been minimal use in our prior trials (< 1%).

**Never-smokers condition.** Women in this condition will be assessed at the study intake assessment, second prenatal care visit, at 28-weeks gestation, and then 2-, 4-, 8-, 12-, 24-, and 48-weeks postpartum using the battery outlined below. As described further below, they will also participate in the sonographic serial measures of fetal growth at 30 and 34 weeks and receive monthly postpartum calls from staff to monitor infant health and health care utilization. There will be no other contact with them.

